#### 1.3. Summarized Risk-benefit Assessment

#### 1.3.1. Known Potential Risks

478

479

480

481

482

483

484

485

486

487

488

489

490

491

492

493

494

495

496

497

498

499

500

501

502

503

504

505

506

In a non-clinical study in SD rats, after 4 consecutive weeks of treatment with TBN for injection, the main adverse reactions observed were slow weight gain, decreased food consumption, decreased animal activity, and the emergence of tachypnea and spasm. The main adverse reactions in beagles, by contrast, were increased muscle tone, decreased food consumption, unstable gait, decreased motor activity, prone and motionless stance, curling up and decreased movement in behavior, loose stools, drooling and decreased thymic weight. Symptoms of toxicity were apparent primarily in the nervous system in the form of altered behavioral activities. With the exception of slow weight gain and decreased food intake, the other toxic effects, such as decreased activity, tachypnea and twitching, were short-lived. No clinical abnormalities were observed during the recovery period. In rats administered for a prolonged period of 26 weeks, a decrease in the weight of the thyroid and parathyroid glands was observed in the ≥50 mg/kg dose group, and diffuse follicular atrophy of the thyroid gland was observed in the ≥50 mg/kg dose group. In beagle dogs administered for a prolonged period of 39 weeks, an increase in alkaline phosphatase was observed in the blood of the males in the 100 mg/kg and 200 mg/kg dose groups.

A total of 128 healthy subjects in completed clinical trials received TBN, including TBN tablets and TBN for injection. The safety and tolerability evaluation included vital signs, physical examination, ECG, and laboratory test. All AEs were recorded. The TBN was safe, with no SAEs, AEs leading to withdrawal from the study, or AEs leading to death or dose-limiting toxicity occurred during the study. Summarized safety for TBN administered orally and intravenously in healthy subjects, drug-related safety information is as follows: The adverse reactions in the single-dose, multiple-dose and food effect study in healthy Chinese human subjects receiving TBN tablets orally included a decreased percentage of neutrophils (1.9%), eruption (1.9%),and increased alanine aminotransferase (1.9%).single-ascending-dose study of healthy subjects receiving TBN for injection intravenously, the adverse reactions included decreased white blood cell count (4.4%), decreased neutrophil count (4.4%), decreased hemoglobin (2.9%), increased blood lactate dehydrogenase (2.9%), decreased percentage of neutrophils (2.9%), decreased hematocrit (1.5%), positive Coombs test (1.5%), decreased mean cellular hemoglobin (1.5%), decreased mean cellular hemoglobin concentration (1.5%). In the multiple-ascending-dose study of healthy subjects receiving TBN for Injection

- intravenously, adverse reactions included increased gamma-glutamyl transferase (4.2%),
- decreased erythrocyte count (4.2%), decreased hemoglobin (4.2%), and decreased erythrocyte
- pressure volume (4.2%).

510

531

#### 1.3.2. Known potential benefits

- The benefits of TBN for ALS treatment include three aspects:
- 512 1) Nonclinical studies have shown that TBN was effective in the treatment of ALS. 10, 30, and
- 513 60 mg/kg of TBN can improve motor behavioral deficits caused by loss of spinal cord motor
- neurons in a mice model of ALS, markedly reduce the expression of SOD1 in the spinal cord,
- and significantly reduce the atrophy of muscle fibers of the gastrocnemius muscle, as well as
- improve the survival of motor neurons in the spinal cord and attenuating astrocyte activation.
- 517 2) TBN has good blood-brain barrier permeability, which is crucial for diseases in central
- 518 nervous system. TBN has strong free radical scavenging ability, which can attenuate
- 519 mitochondrial damage caused by oxidative stress. TBN can inhibit calcium inward flow. TBN
- also has anti-inflammatory activity. TBN can activate the AMPK/PGC1 pathway/Nrf2/HO-1
- 521 pathway, which improves the mitochondrial function, and thus attenuates damage in neuronal
- 522 cell. These properties suggest that TBN is a potential ALS treatment.
- 523 3) The combination of TBN and riluzole is expected to be safe. The two drugs have different
- mechanisms of action (riluzole acts by inhibiting excitatory neuronal activation and TBN acts
- mainly by scavenging free radicals), and it is expected there may be a synergistic effect in
- efficacy. In vitro findings suggesting that the combination of riluzole with CYP1A2 inhibitors or
- 527 inducers may increase or decrease the blood concentration of riluzole, thereby increasing the
- 528 adverse effects of riluzole or affecting its efficacy. The results of nonclinical studies have
- demonstrated that TBN has no inhibitory or inducing activity on CYP1A2. Therefore, drug-drug
- interactions between TBN and riluzole are unlikely to occur.

#### 1.3.3. Potential risk-benefit assessment

- 532 Completed studies suggest that TBN may be safe and effective in the treatment for ALS. The
- 533 investigator will monitor the side effects of TBN. If any side effects or discomfort occur during
- the study, the investigator may use other medications to control it. If the investigator verify that

- the subject cannot tolerate these side effects, TBN administration may be stopped and the subject
- may withdraw from this study.

# 537 **2. STUDY OBJECTIVES**

- 538 To evaluate the efficacy and safety of TBN tablets in patients with ALS, and to explore the
- 539 optimal effective dose.

## 540 **3. STUDY DESIGN**

- 541 **3.1.** Overall study design
- The study is designed to be a multi-center, randomized, double-blind, placebo-controlled study
- of efficacy and safety of TBN tablets for the treatment of ALS.
- 544 3.1.1 Design Rationale
- The design basis of this study is as follows:
- 546 (1) General Considerations for Clinical Trials, NMPA, Jan 18, 2017
- 547 (2) Safety Data Rapid Reporting Standards and Procedures During Drug Clinical Trials, NMPA,
- 548 Apr 27,2018
- 549 (3) Chinese Guidelines for Diagnosis and Treatment of Amyotrophic Lateral Sclerosis, Jul, 2012
- 550 (4) Amyotrophic Lateral Sclerosis Developing Drugs for Treatment Guidance for Industry, Feb,
- 551 2018
- As for the screening of subjects, the sponsor requires that incapacitated subjects should obtain
- the consent of their legal guardians to subjects in the test, and vulnerable groups such as children,
- pregnant women, mentally retarded people, mental patients and prisoners should be given special
- protection according to the Good Clinical Practice (GCP) and Methods for ethical review of
- 556 biomedical research involving human beings promulgated by the National Medical Products
- 557 Administration (NMPA).
- In addition, during the design of the protocol, we fully refer to the NDA clinical trial scheme and

results applied by Edaravone, a drug with similar mechanism of action, for the treatment of ALS. ALSFRS-R was the main endpoint index. Patients with a short duration of ALS (within 2 years from onset) and rapid progression (ALSFRS-R functional score decreased by -1 to -4 points within 3 months of screening period) and mild or moderate ALS (The ALSFRS-R scores are all  $\geq$  2 points when enrolled and the respiratory function is 4 points) and well respiratory function (%FCV  $\geq$  80%) are our target subjects. Compared to the control group, the decline of ALSFRS-R scores in Edaravone group were reduced by 2.5 points after a 6 months treatment period, therefore, the treatment period of TBN is designed as 6 months. We anticipate that TBN tablets can benefit patients with early mild ALS by improving motor dysfunction and delaying disease progression.

#### **3.1.2.** Dose selection rationale

According to the results of efficacy of TBN in the animal model of ALS, PK results of animals and phase I clinical trial results of TBN tablets, the doses are designed to be 600 or 1200 mg per

subject, twice a day.

In the SOD1 mutant ALS mice model, the pharmacodynamic study showed that the efficacy of TBN was demonstrated at 10 mg/kg, and the efficacy of the 30 and 60 mg/kg groups was significant, and the efficacy of the 30 mg/kg group was comparable with that of the 60 mg/kg group. The Cmax of each dose in the rats were  $18 \mu M$ ,  $52 \mu M$ , and  $105 \mu M$ , respectively. In vitro, TBN at  $30\sim300 \mu M$  had excellent free radical scavenging and neuronal protection activities. TBN tablets 1200 mg and 1800 mg were well tolerated in single administration safety, tolerance and pharmacokinetic tests in healthy subjects. 1200 mg and 1800 mg were also well tolerated in multiple administration tests. The pharmacokinetic parameters of TBN tablets in healthy subjects showed that the Cmax of TBN were  $23.85 \mu M$  (5277.57 ng/mL),  $43.31 \mu M$  (9583.79 ng/mL), and  $114.19 \mu M$  (25,271.09 ng/mL) for 400 mg, 600 mg, and 1,200 mg of TBN tablets respectively. The Cmax of 5-OH-TBN (in vitro study showed that its activity was comparable to that of TBN) were  $37.58 \mu M$ ,  $50.8 \mu M$ , and  $110.3 \mu M$ . The dose of TBN administered was linearly correlated with the Cmax range and the Cmax ( $43.31 \mu M$  and  $114.19 \mu M$ ) were calculated for 600 mg and 1200 mg of TBN corresponding to 30 mg/kg, 60 mg/kg TBN Cmax

- 588 (52  $\mu$ M, 105  $\mu$ M) in animals. Therefore the 600 mg and 1200 mg TBN were chosen as low-dose
- and high-dose in this study.

# 590 3.1.3. Definition of the End of Study

- When a subject finish with the last visit in the study schedule or the last study procedure, he/she
- is considered to have completed the study.
- The end of the last visit of the last subject is considered to be the end of the clinical study.

#### **3.1.4. Study Method**

- 595 This study complies the Guidelines for the Good Clinical Practices (GCP) and is designed as a
- 596 multi-center, randomized, double-blind, placebo-controlled study to evaluate the efficacy and
- safety of TBN tablets in patients with amyotrophic lateral sclerosis (ALS). The planed enrolled
- number of subjects in this study are 150. Subjects will be randomly assigned according to the
- ratio: low-dose TBN group: high-dose TBN group: placebo group = 1:1:1. The administration
- time for each patient in this study is about 180 days. This study is an exploratory study, aiming to
- explore the safety and initial efficacy of IMP for the treatment ALS and provide support for
- phase 3 clinical trial.

#### 603 **3.2. Selection of Study Population**

#### 604 3.2.1 Inclusion Criteria

- Subjects will be enrolled into this trial only if they meet all the following criteria:
- 606 (1) Male or female, aged 45 to 70 years old (including 45 and 70 years old).
- 607 (2) Subjects diagnosed with clinically definite or clinically probable ALS according to revised
- El Escorial criteria-1998 by the World Federation of Neurology.
- 609 (3) Subjects of  $\leq 2$  years after the onset of ALS before randomization.
- 610 (4) The ALSFRS-R scores all  $\geq 2$  points, and the respiratory function is 4 points before
- 611 randomization.
- 612 (5) ALSFRS-R has a decrease of 1-4 points during a 3-month screening period.

- 613 (6) Forced Vital Capacity (%FVC) ≥ 80% before randomization.
- 614 (7) Understand and comply with to the study protocol, voluntarily participate, and sign an
- informed consent form (informed consent form is voluntarily signed by the subject
- 616 himself/herself or his/her legal representative).

#### 617 **3.2.2 Exclusion Criteria**

- Subjects who meet one of the following conditions will not be eligible for this trial:
- 619 (1) Familial ALS (judged by family history).
- 620 (2) Those with obvious cognitive impairment (MMSE scale: illiterate group ≤ 19 points,
- primary school group  $\leq$  22 points, junior high school and above group (more than 8 years of
- 622 education)  $\leq$  26 points.
- 623 (3) Obvious dysphagia.
- other known severe renal insufficiency disease.
- 626 (5) Severe liver damage: ALT, AST > 3 times the upper limit of normal level, or other known
- liver diseases such as acute and chronic hepatitis, cirrhosis, etc.
- 628 (6) Acute myocardial infarction or interventional therapy in the past 6 months, heart failure
- patients (in accordance with NYHA classification III-IV patients) at the screening period.
- 630 (7) Combined with malignant tumors and serious diseases of blood, digestion or the other
- 631 systems;
- 632 (8) Allergic to IMP or tetramethylpyrazine.
- 633 (9) Female patients during pregnancy and lactation.
- 634 (10) Participate in other clinical studies within 30 days before screening, or is participating in
- other clinical studies.
- 636 (11)Other circumstances that the investigator considered unsuitable for participation in the study.

#### 3.3 Study Endpoints and Schedule

# 638 **3.3.1 Efficacy Endpoints**

- 639 ✓ Difference between the groups in the ALSFRS-R scores change from baseline at Day 180.
- 640 ✓ Difference between the groups in the proportion of events such as death, tracheotomy,
- invasive ventilator assisted ventilation, or continuous non-invasive ventilator assisted
- ventilation ( $\geq 22$  h per day for  $\geq 10$  days).
- 643 ✓ Difference between the groups in grip strength change from baseline at Day 180.
- of 544 ✓ Difference between the groups in respiratory function (%FVC) change from baseline at day
- 645 180.

637

of 546 ✓ Difference between the groups in ALSAQ-40 scores change from baseline at Day 180.

#### 647 3.3.2 Safety Assessment

- The endpoints consist of treatment-related adverse events (TRAEs), serious adverse events
- 649 (SAEs), clinical laboratory tests (hematology, urinalysis, blood biochemistry, thyroid function),
- of vital signs (blood pressure, respiration, pulse and body temperature), 12-lead electrocardiogram
- 651 (ECG) examination, and physical examination.
- 652 (1) Percentage of participants with serious adverse reactions within 180 days;
- 653 (2) Percentage of participants with adverse reactions within 180 days;
- Record the clinical manifestations, severity, time of occurrence, end time, duration, treatment
- 655 measures and outcomes of AEs and SAEs during clinical study and determine the correlation
- between them and the IMP.

#### **3.4 Concomitant Treatments**

#### 658 **3.4.1** Treatment Compliance

659 IMP and other drug combinations must be documented in the appropriate section of eCRF.

#### 660 3.4.2 Concomitant Illnesses

- Protocol No.: MP-2019-004
- The diseases that existed prior to screening are considered as concomitant diseases and should be
- recorded in eCRF, the following items have to be documented specifically:
- (1) Smoking habits within the last 12 months before screening.
- 664 (2) Alcohol consumption within the last 12 months before screening.
- 665 Concomitant diseases are listed according to the latest edition of the Medical Dictionary for
- Regulatory Activities (MedDRA) in terms of "System Organ Class (SOC)" and "Preferred Term
- 667 (PT)".

## 668 3.4.3 Prohibited Medication

During the trial, there will be no restrictions on other concomitant medication except edaravone.

#### 670 3.4.4 Permitted medications and non-medications

- Riluzole will be a permitted medication during the trial, but it must be used under the guidance
- of the investigator.
- When an adverse event occurs during the trial, such as an abnormal laboratory test such as a
- decreased white blood cell count, it should be closely observed, and according to the Common
- 675 Terminology Criteria for AEs (CTCAE) 5.0, severity grade 1 AEs are usually not treated
- 676 symptomatically in order to observe the extent and reversibility. However, when a grade 2 or
- higher adverse event occurs, it should be treated according to the investigator's judgement, and if
- treated, information such as the drug name, administration route, dosage, and start and end times
- should be clarified and documented on the original record and eCRF. It is recommended to note
- 680 that the concomitant medication is for the treatment of a specific AE/SAE. If the concomitant
- medication is required for other conditions, such as clinical routine diagnosis and treatment
- assistance, the use is recorded as "for clinical routine use" to distinguish from the treatment for
- 683 AEs.
- 684 Concomitant medication/treatment during the trial should be mandatory for the subject and the
- dose should be as stable as possible.
- 686 Coding of concomitant medications will base on WHO (World Health Organization)

- Pharmacopeial Dictionary terminology. The concomitant medications are summarized according
- to the frequency of WHO coded terms.

# 3.5 Study Schedule

689

690

703

#### 3.5.1 Screening Period

- After signing the informed consent form, inclusion and exclusion criteria will be reviewed and
- demographic, medical and allergy history inquiries will be recorded. Height, weight, physical
- examination, vital signs, hematology, urinalysis, blood biochemistry, 12-lead electrocardiogram,
- respiratory function (%FVC), grip strength, MMSE, and ALSFRS-R scale will be performed.
- Women of child-bearing age will undergo a urine pregnancy test.
- 696 During the screening period, twice ALSFRS-R score examinations are performed to confirm that
- the subject meets the inclusion criteria, and the twice ALSFRS-R examinations should be 90  $\pm$ 3
- days apart. If the subject has an ALSFRS-R score examination within 3 months prior to this trial,
- 699 the results can be used as the first ALSFRS-R score during the Screening Period, upon
- 700 presentation of appropriate documentation (e.g., medical records). During the screening period,
- 701 concomitant treatments (medications & non-medications) need to be documented, and AEs and
- 702 SAEs need to be monitored and documented.

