#### 3.5.2 Baseline and randomization

- Screened subjects complete a baseline program that includes: weight, physical examination, vital
- signs, hematology, urinalysis, blood biochemistry, thyroid function, 12-lead electrocardiogram,
- 706 respiratory function (%FVC), grip strength, ALSFRS-R scale, ALSAQ-40 scale, and
- cerebrospinal fluid collection (if consented). Women of child-bearing potential undergo a urine
- 708 pregnancy test. Repeat testing is not required if the same items are checked at baseline and
- screening and the results within 7 days.
- 710 Once inclusion and exclusion criteria have been verified, randomization number will be
- 711 requested for distribution of the drug, and subjects will be instructed on how to take the
- 712 medication at the study center. The first dose of medication will be taken on the day after
- randomization (Day 1). Diary cards will be distributed and subjects will be instructed to record
- 714 concomitant medication and AEs.

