# 5 METHODS FOR REDUCING BIAS: RANDOMIZATION AND BLINDING

#### 5.1 Randomization

975

976

- 977 This study uses Interactive Web Response System (IWRS) to dispense random numbers and
- 978 corresponding IMP. Subjects' random numbers are generated by independent statisticians
- 979 unrelated to the study using SAS 9.4 software or higher version. The subject-drug randomization
- table is in duplicate, sealed and handed over to the main study unit and the sponsor.
- After a 90 day observation period, eligible subjects are to be randomly assigned to high or low
- dose of the IMP group or placebo group (1:1:1). The investigator log into the IWRS system,
- 983 where they are to be given a random number and a drug code.
- In order to ensure that the number of patients in each trial group is similar and the distribution of
- 985 important prognostic factors is balanced, this study uses the minimization method in dynamic
- 986 randomization. The stratification factors are: the diagnostic grade of ALS (clinical diagnosis vs
- 987 clinical diagnosis and laboratory support The diagnostic criteria for clinical diagnosis), the
- 988 change in ALSFRS-R scores during observation period (-1 or -2 vs -3 or -4) and age (<65 years
- 989 vs >65 years).
- 990 Once having been randomly assigned in the study, subjects withdrawing from the clinical trials
- 991 for any reason, regardless of whether or not having been administered with the IMP, will retain
- their random number and the subject will not be allowed to subjects in the trial again.

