# 1368 STATISTICAL ANALYSIS

- Statistical analysis will be carried out under the authorization of the sponsor. The following
- sections describe the statistical methods used for the efficacy and safety analysis of this study. A
- detailed description will be provided in the Statistical Analysis Plan (SAP).
- All statistical analyses will be programmed using SAS 9.4 or higher version software. All
- statistical tests will be performed on a two-sided test.  $P \le 0.05$  will be considered statistically
- significant, and the confidence interval is 95% confidence.

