# 1368 **8.1 Sample Size Estimation**

- The trial is an exploratory study of safety and efficacy, no statistical assumptions will be made
- and no sample calculations.
- This study is expected to enroll a total of 150 subjects, with 50 in each group.

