# 1398 **8.3.3 Primary Efficacy Endpoint Evaluation**

- 1399 The primary endpoint is difference between the groups in the ALSFRS-R score change from
- baseline at Day 180.
- 1401 ALSFRS-R data of each visit in different treatment groups are statistically described by mean ±
- standard deviation and median (minimum and maximum). Comparing with the baseline, the
- paired T test is to be used to compare the within-group before-after differences. Analysis of
- variance (ANOVA) is used for comparing changes before and after treatment in each group, and
- the linear model will include three random stratification factors. The Tukey method-corrected 95%
- 1406 confidence interval for each group's least squares means (LS Means) and Least Squares Means
- Difference is to be calculated according to the model's least squares means (LS Means) to
- compare the statistical differences between the two groups. The model is to be used to further
- investigate the interaction between groups and three random stratification factors. If there is a
- 1410 qualitative interaction, a subgroup analysis of the relevant random stratification factors will be
- 1411 performed.

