# 1412 8.3.4 Analysis of Secondary Efficacy Endpoint

- 1413 The following four secondary efficacy endpoints, the continuous data of each visit in different
- groups will be described using mean  $\pm$  standard deviation and median (minimum, maximum).
- 1415 Comparing with the baseline data, the paired T test is to be used to compare the within-group
- before-after differences. Analysis of variance (ANOVA) is to be used before and after treatment
- between groups. For the first secondary endpoint (endpoint event and disease exacerbation
- event), Kaplan-Meier plots will be used to describe the survival rate of patients without endpoint
- event, and Log-Rank test or non-parametric statistical method is to be used to compare the
- indicators of each group.
- 1421 (1) Proportion of endpoint events, including death, tracheotomy, invasive ventilator-assisted
- ventilation, or continuous non-invasive ventilator-assisted ventilation ( $\geq$  22 h per day for  $\geq$
- 1423 10 days);
- 1424 (2) Difference between the groups in grip strength change from baseline at Day 180;
- 1425 (3) Difference between the groups in respiratory function (%FVC) change from baseline at
- 1426 Day 180;
- 1427 (4) Difference between the groups in ALSAQ-40 scores change from baseline at Day 180.
- 1428 **8.3.5 Safety Assessment**
- Descriptive statistical analysis is mainly to be used to list the AE and SAE, drug-related AE and
- SAE that occurs in this trial, and between-group comparisons are conducted using the  $X^2$  test or
- 1431 Fisher's test.
- 1432 Descriptive statistics are to be used to summarize laboratory tests, vital signs, and
- electrocardiograms, etc. Shift tables are to be used to describe changes in normal/abnormal
- results before and after administration, such as laboratory tests, electrocardiograms, and physical
- 1435 examinations.
- 1436 **8.3.6 Interim Analysis**
- 1437 Not Applicable

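### Section 8.3.4 names no covariate for the Day 180 change in %FVC and grip strength, so pre-randomisation level and decline that the trial already collects go unused and precision may be lost

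*Protocol*

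**What the plan says.** - **First screening** (Protocol 3.5.1; also the trial schedule and 3.6.1): "respiratory function (%FVC), grip strength, MMSE, and ALSFRS-R scale will be performed". The second screening visit repeats only the ALSFRS-R among the efficacy measures.
- **Baseline** (Protocol 3.5.2; also 3.6.2): the list again contains "respiratory function (%FVC), grip strength, ALSFRS-R scale, ALSAQ-40 scale, and" CSF collection.
- **Interval** (Protocol 5.1): "After a 90 day observation period, eligible subjects are to be randomly assigned to high or low" dose or placebo. Section 3.6.1 puts the two ALSFRS-R screening assessments 90 ± 3 days apart.
- **Two exceptions.** A documented ALSFRS-R score from the preceding 3 months may stand in for the first screening score (3.5.1, 3.6.1). A test done at screening within 7 days need not be repeated at baseline (3.5.2, 3.6.2).
- **Analysis of %FVC and grip** (Protocol 8.3.4): a paired t test within groups and, between groups, "Analysis of variance (ANOVA) is to be used before and after treatment". No baseline value, screening value or stratification factor is named.
- **Analysis of the primary endpoint** (Protocol 8.3.3): "the linear model will include three random stratification factors". One of those factors, defined in 5.1, is the ALSFRS-R change over the observation period, in two classes.
- **Size and planning** (Protocol 8.1): "This study is expected to enroll a total of 150 subjects, with 50 in each group"; "The trial is an exploratory study of safety and efficacy, no statistical assumptions will be made". Section 8 refers detail to an SAP that is not at hand.

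**The concern.** In a progressive disease, subjects who were declining faster before treatment may go on declining faster. That between-subject spread then enters the error variance of a 6-month change. A single baseline value carries level. The pair of first-screening and baseline values also carries rate.

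The protocol already treats the run-in change as prognostic for the primary endpoint: it balances on it and puts it in the model. For %FVC and grip it collects parallel data and names no use for them in the analysis. At stake is the width of the intervals for two of the four secondary endpoints, with 50 subjects per arm, in a trial meant to inform phase 3. Validity is not at stake.

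**Working it through.** **No figure to reproduce.** The protocol states no effect size, SD or power for any endpoint. The only check is 150/3 = 50 per arm, which agrees with 8.1. At two-sided 5% and 80% power, 50 per arm detects (1.960 + 0.842) × √(2/50) = 0.560 SD without adjustment.

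**Model (assumed; none of the values is in the protocol).** True level at baseline a, true slope b per month, independent measurement error e with SD m, and a and b uncorrelated. Visits at −3, 0 and +6 months:
- first screening S = a − 3b + e₀
- baseline B = a + e₁
- Day 180 change D = 6b + e₂ − e₁

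**%FVC, middle setting:** SD(a) = 12 points, SD(b) = 2.5 points/month, m = 6 points.
1. Var(D) = 36 × 6.25 + 2 × 36 = 297.
2. Var(B) = 144 + 36 = 180 and Cov(D, B) = −36, so Var(D | B) = 297 − 36²/180 = 289.8. Baseline alone cuts the SE by 1 − √(289.8/297) = 1.2%.
3. Var(S) = 144 + 9 × 6.25 + 36 = 236.25; Cov(S, B) = 144; Cov(D, S) = −18 × 6.25 = −112.5.
4. Given B: Cov(D, S | B) = −112.5 + 36 × 144/180 = −83.7; Var(S | B) = 236.25 − 144²/180 = 121.05.
5. Var(D | B, S) = 289.8 − 83.7²/121.05 = 231.9.
6. Further SE cut from S: 1 − √(231.9/289.8) = **10.5%**. The equivalent sample size is 289.8/231.9 = 1.25 times as large.

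With a constant interval, B together with (B − S) per 30 days spans the same space as B together with S, so the gain is the same in either form.

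**Range of the further SE cut, beyond baseline adjustment**

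| Endpoint | Slope SD per month | Error SD lowest | Error SD middle | Error SD highest |
|---|---|---|---|---|
| %FVC, SD(a) = 12; error 4, 6, 8 | 1.5 | 6.2% | 0.6% | 0.0% |
| | 2.5 | 24.8% | 10.5% | 4.3% |
| | 3.5 | 40.1% | 23.5% | 13.9% |
| Grip, SD(a) = 9 kg; error 1.5, 2.0, 2.5 | 0.5 | 3.0% | 0.1% | 0.3% |
| | 0.8 | 17.0% | 7.4% | 2.7% |
| | 1.2 | 34.8% | 22.2% | 13.6% |

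**Sensitivity of the middle %FVC result.** With SD(a) from 8 to 15 and an intercept-slope correlation from −0.3 to +0.3, it lies between 7.5% and 14.0%.

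**Subjects without a true interval.** If a share f of subjects has the run-in change and the rest contribute nothing to it, the residual variance factor is about 1 − f × ρ², where ρ² = 1 − 231.9/289.8 = 0.20 at the middle setting. For f = 0.75, 0.5 and 0.25 the cut is about 7.8%, 5.1% and 2.5%. The protocol gives no basis for f.

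**Why the gain can vanish.** The error in B enters the run-in change and the on-treatment change with opposite signs. When m is about 0.71 of the SD of the true 180-day change, these errors cancel the slope signal: the raw correlation of the two changes is 0, and the first-screening value adds 0 to 0.7% beyond baseline.

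**The case against.** The case for leaving 8.3.4 alone has five parts.

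- **Covariates for secondary endpoints are SAP detail.** Partly stands. The SAP may add them, and an unadjusted comparison of change is valid under randomisation. But 8.3.4 itself chooses the method, and 8.3.3 shows that this protocol names model terms where it intends them.
- **ANOVA does not rule out model terms.** Stands. Section 8.3.3 also says ANOVA and then adds factors. A reader might infer that 8.3.4 prohibits adjustment; it only leaves the terms unstated.
- **Not every subject has a 90-day run-in.** Stands. A reader might infer that every subject's own decline is discarded, or that first-screening grip serves no purpose for anyone. Neither holds. A subject entering on an earlier documented ALSFRS-R score may have first-screening %FVC and grip close to baseline. Under the 7-day rule one measurement may be both the screening and the baseline value.
- **The size is assumption only.** Stands. The entry criteria (ALSFRS-R decline of 1 to 4 points, %FVC at least 80%, onset within 2 years) may also narrow the spread of slopes. At an error SD of 6 points, the %FVC gain falls to 4.5% at slope SD 2.0 and 0.6% at 1.5.
- **The trial is exploratory with no power target.** True, and it limits the priority. It is not a reason to leave available information unused when the cost is this low.

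**Conclusion.** The point holds as a low-priority efficiency improvement. On the standard route the trial holds two pre-randomisation values of %FVC and grip about 90 days apart, and the analysis that 8.3.4 names uses neither level nor decline as a covariate. There is no bias.

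A reader might infer that precision is certainly lost. The protocol does not support that; precision may be lost. Under the assumed model (baseline SD 12 points for %FVC and 9 kg for grip), the further SE reduction is 0 to 40% for %FVC, with 10.5% at slope SD 2.5 points/month and error SD 6, and 0 to 35% for grip. It falls roughly in proportion to the share of subjects without a true interval, and it is nil where measurement error dominates. In the middle %FVC setting baseline alone gives only 1.2%, so the run-in term is more than a restatement of baseline adjustment. The baseline value and the stratification factors are still the first terms to add.

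**What to change.** In Protocol 8.3.4 (or in the SAP, before unblinding), pre-specify an ANCOVA of the Day 180 change in %FVC and in grip strength with:
1. the baseline value of the same measure;
2. the three stratification factors, as in 8.3.3;
3. the change per 30 days in the same measure from first screening to baseline.

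For subjects without a true run-in interval (an earlier ALSFRS-R score was used, or one measurement serves as both values under the 7-day rule), set term 3 to the overall mean and add a missing indicator. Fix the minimum interval that counts as a true run-in before unblinding; the protocol offers no value for it.

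Cost: wording, one or two extra degrees of freedom for the run-in term and its indicator, and the need to state the missing-covariate rule. No new visits, measurements or subjects.
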